#### 11.5.2 Subgroup Analysis

An exploratory sub-analysis of the main diagnostic accuracy analysis will be undertaken to evaluate variation in accuracy measures in the following subgroups: children; patients with end-organ dysfunction, assessed using SOFA & PELOD-2 (when available) score (for adults and children, respectively); whether antifungal treatment had been administered prior to the research blood sample being obtained; patients with infection due to different Candida species; and patients with candidaemia (vs other types of invasive candidiasis, such as peritonitis). This analysis will be expressed using 99% CI.

Doc No: TM09-LB01 Protocol Version 8.0 Final\_27.05.2021 Page 30 of

## 11.5.3 Latent Class Analysis

This exploratory analysis will be carried out to support the main analysis. Assuming that both of the reference standards explored are imperfect, Bayesian latent class models (LCMs) can be used to estimate prevalence of true disease and sensitivity and specificity of the two reference standards and three index tests from the observed frequencies of each possible combination of test results. This analysis will initially assume conditional independence between the test results, however since there are obvious correlations between the reference standards and also between the two PCR based tests, this analysis will be repeated with plausible assumptions surrounding the correlations between the test results. Estimates for these correlations will be extracted from trial data where possible and cross checked with published knowledge; both fixed and random effects models will also be used to explore all possible correlations. All parameters will be estimated using 95% CIs and sensitivity analysis will be performed around any assumptions made. The results of these models will be compared using Bayesian p-values, deviance information criteria (DIC) and Akaike's information criterion (AIC).

Doc No: TM09-LB01 Protocol Version 8.0 Final\_27.05.2021 Page 31 of

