the reference standard will be proven + probable Candida infection. This helps to overcome the imperfection in sensitivity implicit in using only the definition for proven infection – although this may trade-off some specificity in the reference standard.

Using this approach, we will produce a range for the diagnostic accuracy metrics based on these two reference standards; this reflects uncertainty in the classification of patients resulting from the absence of a perfect reference standard. In the present study, the reference standard comprising proven + probable infection will be particularly useful since certainty in maximising disease detection is a priority when a test may be used to rule-out infection & stop treatment. When future test users consider adopting the index tests, they will be able to consider both the 'optimistic' and pessimistic' accuracy scenarios depending on whether their intended use of the tests is to rule-in or rule-out infection.

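### The latent class analysis treats 'proven' and 'proven + probable' as two correlated tests, although the first is contained in the second by definition

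*Protocol*

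**What the plan says.** Protocol section 11.2 (Statistical Methods) uses two reference standards. The main analysis classifies patients by the consensus definition of proven disease. In a secondary analysis "the reference standard will be proven + probable Candida infection". Of the pair it says that "we will produce a range for the diagnostic accuracy metrics based on these two reference standards".

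Section 11.5.3 (Latent Class Analysis) takes both standards as imperfect. It plans Bayesian latent class models for true prevalence and for the "sensitivity and specificity of the two reference standards and three index tests from the observed frequencies of each possible combination of test results". The first step is stated plainly: "This analysis will initially assume conditional independence between the test results". The same sentence then names dependence between the two standards, and between the two PCR tests, as the reason for a second step, and commits to that step in these words: "this analysis will be repeated with plausible assumptions surrounding the correlations between the test results". Correlation estimates are to come from trial data where possible and be checked against published knowledge, and "both fixed and random effects models will also be used to explore all possible correlations". Sensitivity analyses and comparison by Bayesian p-values, DIC and AIC follow. The section calls the analysis exploratory and supportive.

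**The concern.** The two standards are not two tests that happen to agree. One is part of the definition of the other. A patient who is positive on proven and negative on proven + probable cannot exist. The starting model nevertheless gives that pattern positive probability, and the repeat describes the link as a correlation to be assumed, extracted or borrowed. It is an inclusion, known exactly before any data are seen.

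This matters because section 11.5.3 is where the protocol tries to estimate true prevalence and the accuracy of the standards themselves. Counting the proven result twice pulls the latent class towards patients positive on the reference, which distorts those quantities.

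**Working it through.** The protocol gives no figure for this analysis, so there is none to reproduce. The check has three steps.

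**1. Structure.** Five binary results give 2^5 = 32 patterns. Those with proven = 1 and proven + probable = 0 number 2^3 = 8 and are structurally empty. Write S_P and S_PP for the sensitivities of the two standards. Within the infected class:

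- Under independence, P(proven +, proven + probable −) = S_P × (1 − S_PP). The true value is 0. They agree only if S_P = 0 or S_PP = 1. The same holds in the uninfected class with the false-positive rates.
- With a covariance c, the probability is S_P × (1 − S_PP) − c. It is zero only at c = S_P × (1 − S_PP), which is the largest value c can take.

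Example with S_P = 0.60 and S_PP = 0.85: the bound is 0.60 × 0.15 = 0.09. As a correlation this is 0.09 / √(0.60 × 0.40 × 0.85 × 0.15) = 0.09 / 0.175 = 0.51. The required correlation is therefore not 1, and it changes with the two sensitivities being estimated, so a value fixed in advance will in general miss it. A usual random-effects model gives every pattern positive probability and reaches zero only in a limit.

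**2. Inputs.** From section 11.1: index sensitivity 95%, specificity 92%, prevalence 4%, 1,188 evaluable patients. Assumed, because the protocol does not give them: the accuracy of both standards, and the weaker-test cases. A prevalence of 8% with S_P = 0.50 corresponds to about 0.50 × 8% = 4% proven disease among all patients. In cases A to C the false-positive rate is 0.1% for proven and 5% for proven + probable, and index specificity is 92%.

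- Case A: prevalence 4%, S_P 0.60, S_PP 0.85, index sensitivity 0.95
- Case B: prevalence 8%, S_P 0.50, S_PP 0.75, index sensitivities 0.75/0.70/0.70
- Case C: prevalence 8%, S_P 0.50, S_PP 0.80, index sensitivity 0.60

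**3. Fit.** A two-class model was fitted by maximum likelihood to the exact expected pattern probabilities of nested data. The covariance between the standards was set, in each class, to a fraction of its bound. The last two columns give the patients per 1,188 placed in impossible patterns and the expected lack of fit (G²).

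| Case | Covariance | Prevalence | S_P | S_PP | Index sensitivity | Impossible | G² |
|---|---|---|---|---|---|---|---|
| A | 0 (independence) | 3.9% | 0.625 | 0.886 | 0.947 | 4.1 | 19.2 |
| A | half | 4.0% | 0.630 | 0.857 | 0.951 | 2.6 | 6.7 |
| A | three-quarters | 4.0% | 0.616 | 0.852 | 0.951 | 1.3 | 3.0 |
| B | 0 (independence) | 6.8% | 0.600 | 0.899 | 0.753/0.707/0.707 | 4.9 | 28.8 |
| B | half | 7.5% | 0.567 | 0.804 | 0.751/0.703/0.703 | 5.0 | 14.0 |
| B | three-quarters | 7.8% | 0.534 | 0.771 | 0.752/0.703/0.703 | 3.0 | 6.8 |
| C | 0 (independence) | 6.4% | 0.636 | 1.000 | 0.593 | 0.0 | 11.5 |
| C | half | 7.1% | 0.586 | 0.908 | 0.602 | 2.3 | 8.8 |
| C | three-quarters | 7.6% | 0.546 | 0.850 | 0.599 | 1.9 | 4.8 |

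At the full bound all three cases return the true values with G² = 0. In case C the independence model empties the impossible patterns by pushing S_PP to 1, so a low count there does not show that the model is sound.

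With higher false-positive rates (0.5% and 20%), S_PP 0.80 and index sensitivity 0.60, independence gives index sensitivity 0.558 at 8% prevalence (S_P 0.50) and 0.52 at 4% (S_P 0.60), both too low.

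**Control.** When the two standards are truly independent, the same model returns the truth. With one three-level reference variable, the true values came back in all five scenarios tried. That model has the same number of parameters: 1 + 2 × 2 + 2 × 3 = 11, against 1 + 5 + 5 = 11.

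**The case against.** The protocol does not stop at independence. Its sentence goes on to admit the correlation between the standards and commits to dependent models, sensitivity analyses and comparison of fit. A reader might infer from the opening clause that independence is the planned model. The text does not support that; it is a declared starting point.

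A reader might also infer that no planned dependence model can work. That too goes further than the documents. A fixed-effects model with the covariance between the standards estimated freely goes to its bound on nested data and recovers the truth. Parameterisation and priors are commonly left to a SAP, which is not at hand here. This stands, but it does not close the point. The wording also allows a value assumed from outside or a usual random-effects model, and nothing in it says the impossible patterns will be held at zero. The planned fit criteria may not separate these: at three-quarters of the bound, the expected G² is only 3.0 to 6.8 with 1,188 patients.

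A third tempting inference is that the fault overstates index sensitivity and so flatters a rule-out test. The calculations do not bear this out. Index sensitivity falls slightly in cases A and C, rises by under one point in case B, and falls by 4 to 8 points in the runs with high false-positive rates.

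Finally, the analysis is exploratory, the primary outcome in section 5.1 does not use it, and section 11.2 already reports accuracy under both standards. All of this stands and limits the weight of the point.

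**Conclusion.** The point holds in limited form. By the protocol's own definitions the independence run is false by construction, and the planned repeat is correct only at one boundary value that the protocol does not name. In every run, independence understated prevalence and overstated the sensitivity of both standards.

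At the planning values the effect is small: prevalence 4.0% to 3.9%, proven sensitivity 60% to 62.5%, proven + probable 85% to 88.6%, index sensitivity within 0.5 points. With weaker index tests it is material: prevalence 8% to 6.4%-6.8%, and proven + probable sensitivity from 75%-80% to 90%-100%. No consistent direction can be claimed for index sensitivity, and the primary negative predictive value is unaffected.

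These sizes rest on assumed reference accuracy, conditionally independent index tests, large-sample maximum likelihood and no priors. Priors and dependence between the PCR tests would change them. The structural fault itself needs none of these assumptions, apart from degenerate cases such as a proven + probable sensitivity of exactly 1.

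**What to change.** In every latent class model under section 11.5.3, enter the reference once as a three-level variable: neither, probable only, proven. Fixing the patterns that are proven-positive and proven + probable-negative at zero is equivalent. Derive both standards from it: sensitivity of proven is P(proven | infected); sensitivity of proven + probable is P(proven | infected) + P(probable only | infected); each specificity is one minus the matching sum among the uninfected.

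Keep the dependence term between the two PCR tests. Drop the run with independent reference standards, or label it as illustrative only. Replace the description of the link between the standards as a correlation with a statement that proven implies proven + probable.

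The cost is one recoded variable and one changed likelihood term. No further data are needed and the basic model keeps 11 parameters. If the SAP already specifies this, only the protocol wording needs aligning.

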## 12 DATA MONITORING

#### 12.1 Data Access

Prior to commencement of the study, the PI will give permission for trial related monitoring, audits, ethics committee review and inspections, by providing direct access to source data and trial related documentation. Consent from patients for direct access to data will also be obtained. The patients' confidentiality will be maintained and will not be made publicly available to the extent permitted by the applicable laws and regulations.

## 12.2 Monitoring Arrangements

The CTU will be responsible for trial monitoring. The frequency and type of monitoring will be detailed in the monitoring plan and agreed by the trial Sponsor. Remote and central monitoring activities will be conducted in accordance with the trial monitoring plan and will comply with the principles of Good Clinical Practice (GCP).

The PI or designee should ensure that access to all trial related documents including source documents (to confirm their consistency with CRF entries) are available during any on-site monitoring visits which may take place.

Doc No: TM09-LB01 Protocol Version 8.0 Final\_27.05.2021 Page 32 of

#### 13. TRIAL COMMITTEES

#### 13.1 Trial Management Arrangements

The CI will have overall responsibility for the conduct of the study. The CTU will undertake trial management including all clinical trial applications (Ethics and Research Governance), site initiation/training, monitoring, analysis and reporting. The Trial Co-ordinator will be responsible on a day to day basis for overseeing and co-ordinating the work of the multi-disciplinary trial team, and will be the main contact between the trial team (and other parties involved. Before the trial starts site training will take place to ensure that all relevant essential documents and trial supplies are in place and that site staff are fully aware of the trial protocol and procedures. The CTU will assist and facilitate in the setting up and co-ordination of the trial committees including the Trial Management Group (TMG) and Trial Steering Committee (TSC).

## 13.2 Trial Management Group (TMG)

A Trial Management Group (TMG) will be established and Chaired by the CI. The TMG will have representation on it from the CTU and other investigators/collaborators who are involved in the study and provide trial specific expertise (e.g. trial statistician, health economist). This group will have responsibility for the day to day operational management of the trial, and regular meetings of the TMG will be held to discuss and monitor progress. The discussions of the TMG will be formally minuted and a record kept in the TMF.

A TMG Charter will be drawn up to detail the terms of reference of the TMG including roles and responsibilities.

## 13.3 Trial Steering Committee (TSC)

The conduct of the trial will be overseen by a TSC. The TSC is a group that act as the oversight body for the trial on behalf of the Sponsor/ Funder. Throughout the trial the TSC will take responsibility for monitoring and guiding overall progress, scientific standards, operational delivery and protecting the rights and safety of trial patients.

The TSC will include an independent Chair, not fewer than two independent clinicians/ trialists, a statistician, a patient representative and the CI. Representatives of the Sponsor/Funder and CTU may attend TSC meetings as observers at the discretion of the Chair. The TSC Charter will document the membership of the committee and outline the terms of reference of the TSC including roles/responsibilities, organisation of meetings, reporting, decision making and the relationship with the other trial committees. An inaugural meeting will be held prior to recruitment commencing. Subsequent meetings will be scheduled approaching the end of the internal pilot study and approximately annually thereafter.

Doc No: TM09-LB01 Protocol Version 8.0 Final\_27.05.2021 Page 33 of

## 14. REGULATIONS, ETHICS AND GOVERNANCE

The trial will comply with the principles of GCP, the requirements and standards set out by the applicable regulatory requirements in the UK and the Research Governance Framework.

### 14.1 Sponsorship

Queen's University Belfast (QUB) will act as Sponsor for the study and the CI will take overall responsibility for the conduct of the trial. Separate agreements will be put in place between the Sponsor and each organisation who will undertake Sponsor delegated duties in relation to the management of the study.

#### 14.2 Funding

This study is funded by the National Institute of Health Research (NIHR) Health Technology Assessment Programme, project reference 15/116/03.

#### 14.3 Indemnity

Queen's University Belfast (QUB) as Sponsor will provide indemnity for the management and design of the study. QUB will provide indemnity for negligent and non-negligent harms caused to patients by the design of the research protocol. The NHS indemnity scheme will apply with respect to clinical conduct and clinical negligence.

#### 14.4 Competing Interests

The CI and members of the TMG have no financial or non-financial competing interests. The study is funded by NIHR HTA.

## 14.5 Ethical Approvals

The trial will be conducted in accordance with the ethical principles that have their origin in the Declaration of Helsinki. The protocol will be approved by a Research Ethics Committee.

#### 14.6 Good Clinical Practice

The trial will be carried out in accordance with the principles of the International Conference on Harmonisation Good Clinical Practice (ICH-GCP) guidelines (www.ich.org).

#### 14.7 Protocol Compliance

A protocol deviation is defined as an incident which deviates from the normal expectation of a particular part of the trial process. Any deviations from the protocol will be fully documented on the protocol deviation form in the CRF.

A serious breach is defined as a deviation from the trial protocol or GCP which is likely to effect to a significant degree:

- (a) the safety or physical or mental integrity of the subjects of the trial; or
- (b) the scientific value of the trial

The PI or designee is responsible for ensuring that serious breaches are reported directly to the CTU within one working day of becoming aware of the breach.

Doc No: TM09-LB01 Protocol Version 8.0 Final\_27.05.2021 Page 34 of

Protocol compliance will be monitored by the CTU to ensure that the trial protocol is adhered to and that necessary paperwork (e.g. CRF's, patient consent) is being completed appropriately.

#### 14.8 Protocol Amendments

The investigators will conduct the study in compliance with the protocol given approval/favourable opinion by the Ethics Committee. Changes to the protocol may require ethics committee approval/favourable opinion prior to implementation. The CTU in collaboration with the sponsor will submit all protocol modifications to the research ethics committees for review in accordance with the governing regulations.

#### 14.9 Patient Confidentiality

In order to maintain confidentiality, all study reports and communication regarding the study will identify the patients by the assigned unique trial identifier only. The only exception to this may occur to facilitate the NICTU determining participant mortality by contacting the participant's GP. Computers where information will be stored will be password protected. Patient confidentiality will be maintained at every stage and will not be made publicly available to the extent permitted by the applicable laws and regulations.

#### 14.10 Record Retention

The PI will be provided with an Investigator Site File (ISF) by the CTU and will maintain all trial records according to GCP and the applicable regulatory requirements. The Trial Master File (TMF) will be held by the CTU. On completion of the trial, the TMF and study data will be archived by the CTU according to the applicable regulatory requirements and as required by the Sponsor. Following confirmation from the Sponsor the CTU will notify the PI when they are no longer required to maintain the files. If the PI withdraws from the responsibility of keeping the trial records, custody must be transferred to a person willing to accept responsibility and this must be documented in writing to the CTU and Sponsor.

Doc No: TM09-LB01 Protocol Version 8.0 Final\_27.05.2021 Page 35 of

#### 15. DISSEMINATION/ PUBLICATIONS

#### 15.1 Trial Publications

The final statistical report will be provided by the Trial Statistician; it is anticipated that the study findings will be published in national and international peer reviewed journals and that the preparation of the report will be led by the CI. This will secure a searchable compendium of these publications and make the results readily accessible to the public and health care professionals. In addition study findings may be presented at both national and international meetings and also to appropriate patient groups.

## 15.2 Authorship Policy

Authorship will be determined according to the internationally agreed criteria for authorship www.icmje.org.

## 15.3 Trial Registration

The trial will be registered with the International Standard Randomised Controlled Trial Number (ISRCTN) register.

#### 15.4 Data Sharing Statement

Requests for data sharing will be reviewed on an individual basis by the CI and TMG.

#### 15.5 Data Access

[figure not shown]
Following the publication of the primary and secondary outcomes there may be scope to conduct additional analyses on the data collected. In such instances formal requests for data will need to be made in writing to the CI who will discuss this with the TMG and Sponsor. In the event of publications arising from such analyses, those responsible will need to provide the CI with a copy of any intended manuscript for approval prior to submission. Authorship will need to take the format of "[name] on behalf of the A-Stop Clinical Trial Group" or something similar which will be agreed by the TMG.

Doc No: TM09-LB01 Protocol Version 8.0 Final\_27.05.2021 Page 36 of

## **A-STOP & Newcastle MIC Qualitative Study: Protocol**

# Care pathway analysis of fungal infections in the Intensive Care Unit (ICU)

A qualitative evaluation of the risk preferences regarding the use of rapid diagnostic tests to inform antifungal therapy decision-making for critically ill patients in the ICU: Semi-structured interviews with NHS staff, patients, and legal representatives of patients.

## **Newcastle MIC Work Package**

#### 2.1 Study design

The Newcastle MIC team will perform a set of semi-structured interviews with NHS staff. patients and legal representatives of patients. We will perform interviews with a maximum 30 NHS staff (adult intensivists, paediatric intensivists, microbiologists, laboratory managers, assistant directors from the business/development directorate or equivalent) and a maximum of 10 interviews with patients and legal representatives of patients. The aim of the interviews with NHS staff is to understand the care pathway for fungal infection diagnosis and treatment in the ICU. The aim of the interviews with patients and legal representatives is to understand their, or their dependent's, experience in the ICU and as a participant in the A-STOP trial. The interviews will last between 30-45 minutes for the NHS staff and approximately 30 minutes for the patients and legal representatives of patients. The interviewers will be conducted via video call or phone, whichever is the most convenient for the participant. The data from the interviews will be subjected to qualitative, thematic analysis, and the results will be presented in a report.

